4.2.5 Sensitivity Analyses

We will conduct all analyses described in sections 4.2.1 to 4.2.4 on the ITT population. Analyses of the primary and secondary study objectives will be repeated on the PPA population.

In addition, we will repeat analysis for the primary study objective by using a random-effect structure consisting of GP-level random intercepts nested within practice-level random intercepts to assess for clustering due to GPs working in the same practice.

Sensitivity analyses related to missing data are described in section 4.3.

4.2.6 Subgroup Analyses

We will conduct a subgroup analysis for the baseline HPVv count by repeating the primary outcome analyses on data sets restricted to the categories of baseline HPVv count as defined in section 3.3.1. We will report the estimated coefficients together with 95% confidence intervals.

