2.4 Sample Size

According to the study protocol (2), a sample size of 33 GPs, each recruiting 30 patients, will achieve a power of 80% at an alpha of 5% to detect a coverage change of +9.5% in the control group and of +14.9% in the active intervention group (according to a similar study (3))

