3.1 Confidence Intervals and *p*-Values

We will report statistical significance as determined in statistical null hypothesis tests by means of p-values. A level of significance of 0.05 will be used throughout the analyses. Accordingly, we will report two-sided 95% confidence intervals of coefficient estimates.

We will use a mixed-effects regression model for assessment of the primary objective and we will base rejection of the null hypothesis (no difference in effect on HPVv counts at T6 between the control and

intervention group related to the study hypothesis (see section 1.2) on statistical significance of a specific fixed effect coefficient estimate (see section 4.2.3).

Secondary outcomes will be assessed in an exploratory manner, and no adjustment for multiplicity will be implemented. We will judge resulting *p*-values with appropriate caution and consider the corresponding effect sizes.

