3.3.1 Baseline Data

GPs will be asked to provide the total number of vaccination doses administered during Pb for each of the vaccinations that will also be reported during the study and follow-up periods. GPs will be provided the choice among Never; Rarely (1–5 doses); Occasionally (6–10 doses); Regularly (at least 11 doses). For Pb, no information will be collected on demographic data of patients who obtained the vaccination or on whether the vaccinations were administered as first/second/third doses or booster vaccinations.

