4.2.3 Analysis of the Primary Objective

To analyze the primary objective, we will model the count of first administered HPVv doses at T6 using mixed-effect Poisson regression. The outcome variable will be the count of first HPVv doses administered by each GP at each of the time points T3 or T6. GP-level random intercepts will account for intra-GP correlation. The following fixed effects will define the grouping variables of the data set:

- Study arm (binary with levels control; active)
- Time point (binary with levels T3; T6)
- Baseline HPVv count (categorical with levels Never; Rarely (1–5 doses); Occasionally (6–10 doses); Regularly (at least 11 doses))
- GP gender (binary with levels male; female)
- GP age in years (continuous)
- GP workload (categorical with levels < 60%; 60–79%; 80–100%; based on the distribution of consultation counts according to workload in Swiss primary care (4))
- GP participation status in the cantonal HPVv program at inclusion (binary with levels yes; no)
- Patient gender (binary with levels male; female).

Each fixed effect other than the study arm will be included in the final model if a corresponding univariate analysis results in a *p*-value ≤ 0.2 .

The Poisson regression model will be assessed for overdispersion based on an asymptotic chi-squared test for the sum of squared residuals (5, 6). If the null hypothesis of no overdispersion is rejected at the 0.05 level, we will replace the Poisson model by a negative binomial model with the same fixed- and random-effect structure. A quasi-Poisson model will be considered as an alternative in case of an observed linear variance-to-mean relationship (7).

Rejection of the null hypothesis related to the primary objective (the effect associated with the study arm is equal to zero) will be based on the parameter estimate of study arm and its 95% confidence interval in the final model.

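### The subgroup analysis in SAP 4.2.6 fits the primary model separately in four baseline categories and plans no test of whether the arm effect differs between them

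*SAP*

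**What the plan says.** SAP 4.2.6 describes the subgroup analysis as "repeating the primary outcome analyses on data sets restricted to the categories of baseline HPVv count". The stated output is "We will report the estimated coefficients together with 95% confidence intervals". The categories, from SAP 3.3.1, are "Never; Rarely (1–5 doses); Occasionally (6–10 doses); Regularly (at least 11 doses", so there are four subsets.

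The analysis being repeated is that of SAP 4.2.3. Its fixed effects include "Study arm (binary with levels control; active" and, as a separate entry, "Baseline HPVv count (categorical with levels Never; Rarely (1–5 doses); Occasionally (6–10 doses); Regularly (at least 11 doses". Both are main effects and no product term is listed. Covariates are screened: "Each fixed effect other than the study arm will be included in the final model if a corresponding univariate analysis results in a" p-value of at most 0.2. A test for overdispersion can then replace the Poisson model by a negative binomial one, with quasi-Poisson as a further option. The null hypothesis is judged on the arm estimate and its 95% CI.

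SAP 3.1 adds "A level of significance of 0.05 will be used throughout the analyses". The trial size in SAP 2.4 is "a sample size of 33 GPs, each recruiting 30 patients". The SAP does not say whether 33 is the total or the number per arm.

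**The concern.** A subgroup analysis is run to learn whether the treatment effect differs between categories. The plan yields four estimates, each set against no effect, and nothing that sets them against one another. A CI that excludes no effect among low-baseline GPs but not among high-baseline GPs is not evidence that the two effects differ, yet it is the contrast this output puts in front of the reader.

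A second issue depends on how 4.2.6 is read. If repeating the primary analysis includes rerunning the p-value screen and the overdispersion switch in each subset, the four coefficients may come from different covariate sets or model families. They would then be harder to compare even informally.

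At stake is a false or missed statement about which GPs benefit from the educational session. The primary conclusion is not at stake.

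**Working it through.** The SAP gives no figure for the subgroup analysis, so there is none to reproduce. The check is whether a heterogeneity test is planned anywhere, and then how often the planned output would mislead under stated assumptions.

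**1. Is there a test?** SAP 4.2.6 names only coefficients and CIs. SAP 4.2.3 has arm and baseline count as main effects. SAP 4.2.4 and 4.2.5 add secondary models, a per-protocol repeat and a practice-level random effect, but no interaction. SAP 3.1 discusses multiplicity only for secondary outcomes.

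**2. Size of a subset.** With an even split (an assumption), 33/4 = 8.25 GPs per category if 33 is the total, or 66/4 = 16.5 if 33 is per arm. That is about 4 or 8 GPs per arm in each category.

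**3. No effect in any category, exact 5% tests, independent subsets.** P(at least one of four CIs excludes no effect) = 1 − 0.95⁴ = 1 − 0.8145 = 0.1855, about 18.5%.

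**4. Same true effect in every category, 80% power overall.**
- Overall noncentrality: 1.960 + 0.842 = 2.802.
- A quarter of the information gives 2.802/√4 = 1.401 per category.
- Power per category: Φ(1.401 − 1.960) + Φ(−1.401 − 1.960) = 0.288.
- P(some significant, some not) = 1 − 0.288⁴ − 0.712⁴ ≈ 1 − 0.007 − 0.256 = 0.737, about 74%.

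So when the effect is the same everywhere, a mixed pattern is the likely result. An interaction test in that setting has a nominal false-positive rate of 5%.

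**5. Small-sample Wald CIs.** Steps 3 and 4 assume exact tests. Simulations with no effect used a Poisson model with GP intercept, arm only, equal category sizes and mean counts of 2, 4, 8 and 12. The share of trials with at least one of four CIs excluding no effect was:

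| GP log-SD (assumed) | 4 GPs per arm per category | 8 GPs per arm per category |
|---|---|---|
| 0.2 | 21% | 24% |
| 0.4 | 28% | 28% |
| 0.7 | 51% | 34% |

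Each cell rests on 200 runs. Further runs at log-SD 0.7 gave 43% and 46% with 4 per arm, and 37% and 36% with 8 per arm. The SAP gives neither the log-SD nor the mean counts.

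**6. Power of the joint interaction test.** Let the effect rise linearly across the four categories as 0, 2/3, 4/3 and 2 times the average. The category noncentralities are 0, 0.934, 1.868 and 2.802, with mean 1.401. The sum of squared deviations is 1.963 + 0.218 + 0.218 + 1.963 = 4.36. Power is P(noncentral χ² with 3 df and noncentrality 4.36 > 7.81) = 0.388, about 39%.

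**The case against.** Several points on the other side have force.

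- **A reader might infer that the plan makes heterogeneity impossible to assess.** It does not. The subsets contain different GPs, so a heterogeneity statistic can be computed from the four reported coefficients and CIs. SAP 4.2.6 sets no significance rule for the subsets and claims no effect modification. SAP 2.2 also stratifies randomization by these same categories, so the within-category arm comparisons have support in the design. What stands is that no formal comparison is planned.
- **A reader might infer that the four coefficients are bound to be non-comparable.** SAP 4.2.6 does not say whether the screen is rerun in each subset or the already selected model is refitted. Rerunning is plausible but is not the only reading.
- **A reader might infer that the subset models cannot be fitted.** Intercept, arm, GP gender, age, two workload terms and programme status make up to 7 GP-level coefficients against perhaps 8 GPs. However, SAP 4.2.4 allows models to be adapted, for example by dropping ill-defined variables, although it does not name subgroup fits.
- **The higher simulated figures should not be taken as the size of this defect.** They mix in Wald CIs that are too narrow with few GPs: at log-SD 0.7 and 4 per arm, single-category rejection was 7% to 18% instead of 5%. They fall to about 21% at log-SD 0.2. Nor should they be set against the rejection rate of an interaction test, which tests a different null hypothesis.
- **The remedy is imperfect.** In simulation at log-SD 0.7 with no effect, the joint test rejected 8.8% (chi-square) and 6.0% (F reference) with 4 GPs per arm per category, and 10.7% and 8.7% with 8 (300 runs, so Monte Carlo error is sizeable). Its power is low, and a common GP variance and common covariate effects are added assumptions.

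These points limit how strongly the issue can be put. None of them supplies the missing comparison.

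**Conclusion.** The point holds in limited form. As written, SAP 4.2.6 produces four arm effects and no assessment of whether they differ. Under four equal categories and exact 5% tests, the figures are 18.5% for at least one apparently significant category when there is no effect, and 74% for a mixed pattern when the effect is the same everywhere. With Wald CIs the first figure was about 21% to 51% in simulation, depending on an assumed GP log-SD between 0.2 and 0.7. Possible differences in covariates or model family between subsets are conditional on the screen and the overdispersion switch being rerun. The analysis lies outside the primary and secondary objectives in SAP 4.1, and the primary test does not depend on it. The change is worth making because it is cheap, not because the trial's main result is threatened.

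**What to change.** In SAP 4.2.6, replace the four restricted fits by one model on all GPs:

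- Take the primary model with baseline category and arm × baseline category, both forced in whatever the p-value screen says, and use one common covariate set and one model family.
- Report the joint interaction test (3 df, with a small-sample reference distribution) as the subgroup result, and the four category-specific rate ratios with CIs from that same model.
- Collapse adjacent categories when a category-by-arm cell is empty or has only zero counts, and reduce the degrees of freedom to match.
- Label the analysis exploratory and state that the interaction test has low power, so a non-significant result does not show that the effect is the same in all categories.

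The cost is a few sentences of SAP text and one additional fit, with no new data. The four estimates that 4.2.6 asks for are still delivered. The price is low power and the assumption that covariate effects and the GP variance are common across categories.

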4.3 Missing Data

Missing data may potentially occur on two levels:

- GPs: baseline (including demographic) characteristics, failure to undergo the intervention, failure to return CRFs (including loss to follow-up) or questionnaires.
- Patients (data from the CRFs): demographic characteristics, type of vaccination.

To analyze the study objectives, we will use the following procedures to handle missingness in the ITT and PPA population data sets:

- Loss to follow-up of GPs: complete-case analysis.
- Missing baseline characteristics of GPs and missing patient-level characteristics: complete-case analysis.

For each study objective, we will conduct a sensitivity analysis on the IIT population using multilevel chained equations-based multiple imputation with 5 datasets and 20 iterations. We will restrict use of multiple imputation to this sensitivity analysis and use a complete-case approach for the main analysis due to the low anticipated drop-out rates (2).

For other analyses not belonging to a study objective, we will handle missing data by pairwise deletion (i.e., by omitting only cases with missing values of variables relevant to the current analysis).

The nature and frequency of missing data will be reported for all analyses. Differences in loss to followup frequencies between the study arms will be assessed using Pearson's chi-squared and Fisher's exact test.

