2.8 Timing of Study Assessments

For each GP included into the study, we define the following timings:

- Baseline period Pb: A consecutive period of three months as recent as possible, but entirely before the intervention date Ti. Study participants will be asked to provide estimates of the number of HPVv doses administered during this period, which will be used for stratified randomization (see sections 2.2 and 3.3.1).
- Intervention date Ti: The day of delivery of the active and control intervention in the active intervention arm or of the control intervention in the control intervention arm. A questionnaire assessing knowledge on HPV and attitudes concerning HPVv will be administered at Ti, right before delivery of the intervention.
- Study start T0: The day of start of vaccination counting, usually scheduled on the 1st of the respective month following Ti. If Ti falls within the first week of a month, T0 is usually scheduled on the 15th of the same month.
- Follow-up at T3, T6, and T12: The dates at three, six and twelve months, respectively, after the study start T0. The questionnaire on HPV knowledge and HPVv attitudes will be delivered a second and final time at T6.
- **Study period**: The time interval between T0 and T6, which is the time interval relevant to the primary objective of the study.
- Follow-up period: The time interval between T6 and T12.
- Study end: The follow-up date T12, which indicates the end of all vaccination documentation.

3 Statistical Principles

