3.2 Analysis Populations

For each of the primary and secondary objectives, we will define an intention-to-treat analysis (ITT) population as the population of all GPs who underwent randomization, regardless of participation in the educational session at Ti and loss to follow-up.

For each of the primary and secondary objectives, a per-protocol analysis (PPA) population will include all GPs who participated in the educational session at Ti.

Handling of missing data in the ITT and PPA populations is described in section 4.3.

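### The SAP sets no counting window for randomised GPs who miss the session and lists non-attendance as missing data, so the main ITT analysis may lose them

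*SAP*

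**What the plan says.** **Populations (SAP 3.2).** ITT is all randomised GPs, "regardless of participation in the educational session at Ti and loss to follow-up". By contrast, "a per-protocol analysis (PPA) population will include all GPs who participated in the educational session at Ti". Section 4.2.5 makes ITT the main analysis and repeats the analyses of the objectives on the PPA population.

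**Timing (SAP 2.8).** The dates are set GP by GP: "For each GP included into the study, we define the following timings". The first is "Intervention date Ti: The day of delivery of the active and control intervention in the active intervention arm", with the corresponding control session in the other arm. T0 is then "The day of start of vaccination counting, usually scheduled on the 1st of the respective month following Ti", with the 15th of the month as the usual alternative after an early-month session. T3, T6 and T12 are counted from T0. The study period is "The time interval between T0 and T6, which is the time interval relevant to the primary objective of the study".

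**Missing data (SAP 4.3).** The GP-level sources are baseline characteristics and "failure to undergo the intervention, failure to return CRFs (including loss to follow-up) or questionnaires". Two complete-case rules follow, one for loss to follow-up and one for missing GP baseline or patient-level characteristics. They apply to both populations. The section describes the main analysis as complete-case. Multilevel multiple imputation on the ITT population is confined to a sensitivity analysis for each objective.

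**The concern.** A GP who is randomised and then misses the session is non-adherent. That GP's vaccination counts can still be observed, and an ITT analysis needs them. The SAP accepts this in 3.2, but elsewhere gives such a GP no date from which to count and places the missed session among the missing data. Attendance is not a variable in the primary model (4.2.3). For the vaccination counts, calling it missing data therefore has an effect only if the GP's outcome is taken to be missing.

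Two things are at stake. The main analysis could be a comparison of attenders under an ITT label. The PPA repeat in 4.2.5 would then use the same GPs and show nothing about the influence of non-attendance. The question differs from that of GPs who attend and later stop returning CRFs, which 4.3 lists separately and gives its own rule.

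**Working it through.** No figure in the SAP measures non-attendance, so there is nothing to reproduce. The check is mainly one of definitions.

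**Step 1: is there a window for a non-attender?** The chain in 2.8 runs from session delivery to Ti, from Ti to T0, and from T0 to T6. No step supplies a date when a GP is absent. The word *usually* in the T0 definition gives latitude over the calendar day, but a Ti is still needed to start from.

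**Step 2: what rule in 4.3 applies?** Non-attendance is listed as a source of missing data. Neither complete-case rule names it. The only general statement about the main analysis is that it is complete-case.

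**Step 3: which GPs are analysed?** Let N be the number randomised and d the share who miss the session. Leave aside other missingness, which 4.3 handles alike in both populations.

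- *Reading A: non-attenders have no T0 and no counted outcome.* The complete-case ITT analysis keeps N(1 − d) GPs, and so does the PPA.
- *Reading B: T0 is taken from the scheduled session and non-attenders return CRFs.* The ITT analysis keeps N and the PPA keeps N(1 − d).

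Section 2.4 gives 33 GPs without saying whether this is the total or per arm. The rates d are assumed.

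| d (assumed) | N = 33: N(1 − d) | N = 66: N(1 − d) |
|---|---|---|
| 0 | 33 | 66 |
| 5% | 31.3 | 62.7 |
| 10% | 29.7 | 59.4 |
| 20% | 26.4 | 52.8 |

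Under reading A these are the sizes of both the ITT and the PPA analysis. Under reading B they are the sizes of the PPA only. The SAP does not say which reading applies. If everyone attends (d = 0), the sets coincide harmlessly.

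**Step 4: illustration of a possible effect.** All inputs are assumed: a rate ratio of 1.5 among attenders, a share p of active-arm GPs missing the session, none missing in the control arm, and non-attenders vaccinating at the control rate.

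ITT ratio = 1.5(1 − p) + 1 × p = 1 + 0.5(1 − p)

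- p = 0.10: 1 + 0.5 × 0.90 = 1.45
- p = 0.20: 1 + 0.5 × 0.80 = 1.40

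An analysis of attenders only would report 1.50. The excess over control would be overstated by a factor of 0.50/0.45 = 1.11 to 0.50/0.40 = 1.25.

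**The case against.** The strongest reply is that the SAP can be read so that nothing is lost.

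- Section 3.2 speaks of participation in the session at Ti, which presupposes a Ti for GPs who did not take part. Ti could simply be the session date.
- Section 3.3.2 provides CRFs to enrolled GPs, not only to attenders. Nothing says that non-attenders are not followed.
- Neither complete-case rule names non-attendance, and attendance is not in the primary model. A non-attender with CRFs and covariates is a complete case.
- The entry in 4.3 may have an ordinary purpose. The questionnaire is given at Ti, just before the session, so a GP who misses the session may lack the baseline scores for secondary objectives 4 and 5.
- The imputation analysis on the ITT population would retain non-attenders.

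Most of this stands. A reader might infer that the ITT analysis necessarily collapses into the per-protocol analysis. The SAP does not say so, and that conclusion requires two inferences: that non-attenders have no counted outcome, and that they are therefore deleted.

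The reply does not remove the conflict. Section 2.8 says day of delivery, and reading it as a scheduled date means correcting the text. Section 4.3 lists a missed session apart from unreturned CRFs and questionnaires, and does not limit the entry to questionnaire scores. The imputation is only a sensitivity analysis. If no counts are collected from non-attenders, it must borrow from attenders, and with arm in the model it would tend to carry the attenders' effect over to them.

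**Conclusion.** The point holds as a conflict between 3.2 on one side and 2.8 and 4.3 on the other. Applied literally, the wording may drop randomised GPs from the main ITT analysis and leave the PPA repeat uninformative. It should be corrected before the SAP is approved.

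Its size cannot be derived from the SAP, which gives no non-attendance rate. A reader might take the 11% to 25% overstatement as an estimate of bias. It is arithmetic on assumed inputs and also assumes that only the active arm has non-attenders. A reader might also infer that attenders in the two arms differ in motivation for HPV vaccination, since only control GPs are fully blinded to the HPV topic (2.3). The SAP does not say that active-arm GPs learn the topic before they attend, so this is possible but not shown.

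**What to change.** 1. In 2.8, define Ti for every randomised GP as the date of the session scheduled for the GP or the practice, attended or not. T0 to T12 then follow by the existing rules.
2. State in 2.8 or 3.3.2 that CRFs are collected from non-attenders over that window and their counts used.
3. In 4.3, remove failure to undergo the intervention as a source of missing outcome data. A Ti questionnaire not completed because the GP was absent remains missing data for secondary objectives 4 and 5.
4. State that these GPs stay in the ITT analysis and are excluded only from the PPA.

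The cost is a few sentences in the SAP and a few additional CRFs. The effect estimate may become slightly smaller, because GPs who did not receive the session are counted in the arm to which they were randomised.

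### Complete-case handling of missing patient sex removes documented first doses from the primary count, and the rule for GPs lost to follow-up leaves open whether their observed T3 data are discarded

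*SAP*

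**What the plan says.** Section 4.2.3 of the SAP defines the primary outcome: "The outcome variable will be the count of first HPVv doses administered by each GP at each of the time points T3 or T6". The model is a mixed-effects Poisson regression with GP random intercepts. The listed fixed effects also define how the data set is grouped, and one of them is "Patient gender (binary with levels male; female"). There is no level for unknown. Every fixed effect except study arm stays in the final model only if its univariate p-value is at most 0.2.

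Section 4.3 expects gaps in the patient data: "Patients (data from the CRFs): demographic characteristics, type of vaccination". For the main analysis it sets two rules: "Loss to follow-up of GPs: complete-case analysis" and "Missing baseline characteristics of GPs and missing patient-level characteristics: complete-case analysis". The reason given is low anticipated drop-out, without a figure. Multilevel multiple imputation is planned for every objective, but only as a sensitivity analysis. The section also promises to report the nature and frequency of missing data and to compare loss to follow-up between arms.

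Section 3.2 defines ITT as "the population of all GPs who underwent randomization, regardless of participation in the educational session at Ti and loss to follow-up" and adds: "Handling of missing data in the ITT and PPA populations is described in section 4.3". Section 4.2.5 runs the main analyses on that population.

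**The concern.** In most regressions, deleting an incomplete record removes an observation. Here the records are doses and the outcome is their number, so deleting a record changes the outcome value. A dose that the GP wrote on the form and that belongs to the primary outcome is lost because an unrelated field is blank. The reason given for complete-case analysis, low drop-out, concerns GPs leaving the study and says nothing about blank fields on paper forms.

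Unequal completeness between arms is conceivable. Under sections 2.1.2 and 2.3, active-arm GPs receive HPV-specific teaching while control GPs are kept unaware that HPV vaccination is the topic. If care in filling in HPV entries differed as a result, the difference would enter the rate ratio directly.

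The rule for lost GPs raises a related problem. If it removes the whole GP, data already collected are discarded, and the analysis labelled ITT rests on completers. If drop-out is related to how many doses a GP gives, the rate ratio moves as well.

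**Working it through.** The SAP states no missing-data rate, so there is no plan figure to reproduce. All rates below are assumptions.

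**1. What happens to a dose without sex.** The data set has cells by GP, time point and patient gender (male, female). A dose with blank sex belongs to neither cell, and complete-case analysis does not assign it to one. If a share m of an arm's documented first doses lacks sex, that arm's analysed count is (1 − m) times its documented count: 0.95 at m = 5%, 0.90 at m = 10%.

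**2. Effect on the arm rate ratio.** Multiplier = (1 − m_active)/(1 − m_control).

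| Missing, control | Missing, active | Multiplier |
|---|---|---|
| 5% | 5% | 0.95/0.95 = 1.00 |
| 10% | 10% | 0.90/0.90 = 1.00 |
| 5% | 10% | 0.90/0.95 = 0.947 |
| 10% | 5% | 0.95/0.90 = 1.056 |
| 5% | 20% | 0.80/0.95 = 0.842 |
| 20% | 5% | 0.95/0.80 = 1.19 |

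The counts fall in every row. The ratio moves only when the shares differ, and it can move either way.

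**3. Whether the primary model needs patient gender.** Write the mean for GP i and gender g at a given time point as exp(a_i + b·arm_i + c_g), with a_i the GP intercept. The GP's total is then Poisson with mean exp(a_i + b·arm_i) × (exp(c_male) + exp(c_female)). The second factor is a constant that the overall intercept absorbs. Given the total, the split by gender is binomial with probability exp(c_female)/(exp(c_male) + exp(c_female)), which does not contain b. With all GP-by-gender cells present, zeros included, the gender split therefore carries no information on the arm effect. The identity is exact for the Poisson model but not for the negative binomial fallback.

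**4. A GP who stops after month 4.** Forms are mailed every two months (section 3.3.2), so this is a realistic stopping point. The T3 count is then fully observed. The T6 row has 4 of 6 months documented if it counts from T0, or 1 of 3 if it counts from T3. There are two readings of the complete-case rule:
- By row: the T3 row stays and the T6 row goes.
- By GP: both rows go, and 4 documented months are lost.

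Section 4.3 contrasts complete-case analysis with pairwise deletion for other analyses, which makes the second reading a natural one, but it does not say which is meant.

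**5. What whole-GP deletion could do.** This was simulated with gamma-Poisson counts (assumed mean 3 in control and 4.5 in active, true ratio about 1.50). GPs with no first dose by T3 dropped out with a set probability and were removed whole.

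| Drop-out probability of zero-count GPs, control / active | Ratio among GPs kept |
|---|---|
| 30% / 30% | 1.46 |
| 30% / 10% | 1.42 |
| 50% / 10% | 1.34 |
| 10% / 30% | 1.55 |

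On precision alone, an assumed loss of 10% of GPs widens the interval by 1/√0.9 = 1.054, about 5%.

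**The case against.** Five points can be made for the plan.

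- **Gender is only a candidate.** It stays in the final model only at p ≤ 0.2, and if it is dropped the counts could be rebuilt without it. That is true. But section 4.2.3 makes it a grouping variable of the data set, the plan does not say that counts are rebuilt, and whether a documented dose counts should not depend on a screening p-value.
- **Bias in the treatment effect is not shown.** A reader might infer that the rate ratio is biased. The documents do not support this: they give no missing rates and no evidence that completion of the sex field differs by arm. Section 2.3 has forms that ask about all vaccinations without emphasis on HPV, and section 3.3.2 asks for age and sex for all of them. The shift in the ratio is conditional.
- **Whole-GP deletion is not stated.** A reader might infer that every GP lost before T6 is discarded. A row-wise reading fits the T3/T6 mixed model equally well. What stands is that the SAP does not settle it.
- **The ITT definition is not contradicted.** A reader might infer a contradiction, because section 3.2 includes GPs regardless of loss to follow-up. But that section defines membership and refers missing data to section 4.3, so the handling is disclosed. What stands is that, on the GP-wise reading, ITT describes the population and not the GPs who decide the test.
- **Imputation on the ITT population is planned for every objective.** This is a real safeguard, as is the promised reporting of missing data. It does not change the primary test, which rests on the complete-case fit.

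**Conclusion.** The point holds in limited form. As written, sections 4.2.3 and 4.3 together remove documented first doses from the primary outcome when patient sex is blank. The understatement of the counts is certain wherever sex is missing and the data set is split by gender. Its size equals the missing share, which the SAP does not give. The effect on the rate ratio is conditional: 0.947 to 1.056 for assumed shares of 5% and 10% in opposite arms, 0.84 to 1.19 for 5% and 20%, and none if the shares are equal.

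The treatment of GPs lost before T6 is an ambiguity that needs closing. Under whole-GP deletion with count-dependent drop-out, the simulated ratio moved from about 1.50 to between 1.34 and 1.55, under assumed counts and drop-out rates. The sponsor should correct the text before analysis, since the deletion of doses gains nothing.

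**What to change.** In section 4.3, state that every documented first HPV dose enters the GP's total whether or not patient age or sex is recorded. In section 4.2.3, take patient gender out of the primary model and analyse GP totals by time point, keeping gender for the descriptive objectives. Under the Poisson model this loses no information on the arm effect. Under the negative binomial fallback the results are not identical, but the GP total remains a well-defined outcome.

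State that all observed T3 and T6 rows of every randomised GP with any returned form are kept, with the log of documented time in the interval that the row covers as an offset.

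Keep the complete-case fit and multiple imputation as sensitivity analyses. Imputation should also cover what the main rule cannot: doses whose dose number is missing, so that it is unknown whether they are first doses, and randomised GPs who return no form.

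The cost is SAP wording, with no new data to collect. The one added assumption is a constant rate over a GP's undocumented time, which the imputation analysis can probe.
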